### SCHEMA

The primary endpoint is end of treatment complete remission rate

#### Abbreviations:

AD: Adriamycin, Dacarbazine

CR – Complete Response

PR – Partial Response

SD – Stable Disease

PD – Progressive Disease

---

CONFIDENTIAL

This document is confidential. Do not disclose or use except as authorized.

## **1. OBJECTIVES**

### **1.1 Study Design**

This is an open label single arm phase II study to assess the efficacy and safety of Brentuximab Vedotin (hereafter referred to as brentuximab) in combination with Adriamycin and Dacarbazine (AD) in patients with previously untreated stage I and II non-bulky classical Hodgkin lymphoma (cHL). All patients will receive combination therapy with brentuximab and AD with all agents administered on days 1 and 15 of each 28 day cycle. Brentuximab will be administered at 1.2 mg/kg. AD will be administered at standard doses (Adriamycin 25mg/m^2, Dacarbazine 375 mg/m^2). Interim restaging PET-CT will be performed following cycle 2. Patients with progressive disease will be taken off study. Patients in CR will receive a total of 4 cycles of therapy; patients with stable disease or partial response will receive a total of 6 cycles. There is no planned radiotherapy for patients achieving a complete remission at the end of therapy.

### **1.2 Primary Objective**

- 1.2.1 To investigate the clinical activity of Brentuximab with AD in untreated non-bulky stage I and II Classical Hodgkin Lymphoma (cHL)

### **1.3 Secondary Objective**

- 1.3.1 To describe the safety and tolerability of Brentuximab combined with AD in previously untreated non-bulky limited stage cHL

### **1.4 Endpoints**

- 1.4.1 Primary: Complete response rate (CRR) at end of treatment restaging, by the revised International Working Group Criteria (see appendix A)
- 1.4.2 Secondary:
- Rate of grade III and IV adverse events or discontinuation due to toxicity
  - Overall response rate (ORR) at end of treatment restaging
- 1.4.3 Exploratory:
- Failure-free survival (FFS)
  - Overall survival (OS)

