We conducted a phase 2 study of 34 patients with non-bulky limited stage classical Hodgkin lymphoma, which completed accrual in 2014. Though data are immature, the treatment appeared highly effective and overall well tolerated. Preliminarily, all patients achieved complete response after 2 cycles of combination brentuximab-AD and no patients required more than 4 cycles of combination chemotherapy. One patient did relapse after achieving remission and was successfully treated with second-line therapy. One additional patient developed neutropenic sepsis and died in remission during therapy. An initially high rate of neutropenic fever was observed, prompting a protocol amendment requiring the use of GCSF support, after which the incidence of infection and neutropenic fever was much lower.

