### 6.1 Anticipated Toxicities for Brentuximab, Adriamycin, Dacarbazine

#### 6.1.1 Anticipated Toxicities for Brentuximab

A list of the adverse events and potential risks associated with the agents administered in this study appear below. Most toxicities related to brentuximab in the phase I and II studies were Grade 2 or less. A table detailing the Grade 3 toxicities in the phase II studies is below.

Peripheral neuropathy has been commonly reported in the phase II with 44% of patients having peripheral sensory neuropathy, and 9% peripheral motor neuropathy. Of these only 11% were Grade 3 and there were no Grade 4 events. The neuropathy was reversible in nearly all patients with median resolution of 6.6 weeks.

Neutropenia occurred in 21% of patients in the phase II studies with 20% of patients  $\geq$  Grade 3 (13% Grade 3 and 7% Grade 4). Neutropenia  $\geq$  Grade 3 tended to develop after a median of 2 doses and lasted a median of approximately 1 week. Of the 7% of patients with Grade 4 neutropenia, only 3 had neutropenia that lasted  $\geq$  7 days.

Additional toxicity data is as follows:

**Treatment-emergent adverse events  $\geq$  Grade 3 occurring in  $\geq$ 2 HL or systemic ALCL patients in the phase 2 population (Studies SG035-0003 and SG035-0004)**

	HL SG035-0003 (N=102)			ALCL a SG035-0004 (N=58)		
	n (%)			n (%)		
	Grade			Grade		
	$\geq$ 3	4	5	$\geq$ 3	4	5
Any event	56 (55)	14 (14)	1 (1)	35 (60)	9 (16)	6 (10)
Neutropenia	20 (20)	6 (6)	0	12 (21)	5 (9)	0
Thrombocytopenia	8 (8)	2 (2)	0	8 (14)	3 (5)	0
Peripheral sensory neuropathy	8 (8)	0	0	6 (10)	0	0
Anaemia	6 (6)	1 (1)	0	4 (7)	0	0
Hyperglycaemia	4 (4)	0	0	1 (2)	0	0
Fatigue	2 (2)	0	0	2 (3)	1 (2)	0
Abdominal pain	2 (2)	1 (1)	0	1 (2)	0	0
ALCL recurrent	0	0	0	3 (5)	0	3 (5)
Diarrhoea	1 (1)	0	0	2 (3)	0	0
Hypokalaemia	1 (1)	0	0	2 (3)	0	0
Peripheral motor neuropathy	1 (1)	0	0	2 (3)	0	0
Pulmonary embolism	2 (2)	2 (2)	0	1 (2)	0	0
Pyrexia	2 (2)	0	0	1 (2)	0	0
Syncope	2 (2)	0	0	1 (2)	1 (2)	0
Urinary tract infection	1 (1)	0	0	2 (3)	0	0
Anxiety	2 (2)	0	0	0	0	0
Deep vein thrombosis	0	0	0	2 (3)	0	0
Demyelinating polyneuropathy	2 (2)	0	0	0	0	0
Hodgkin's disease recurrent	2 (2)	0	1 (1)	0	0	0
Mycosis fungoides	0	0	0	2 (3)	0	0
Pain in extremity	0	0	0	2 (3)	1 (2)	0
Pneumonitis	2 (2)	1 (1)	0	0	0	0
Pyelonephritis	2 (2)	0	0	0	0	0
Vomiting	0	0	0	2 (3)	0	0
Weight decreased	0	0	0	2 (3)	0	0

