##### 13.1.1 Primary Endpoint and Sample Size

The primary endpoint of this study is complete response rate at EOT restaging. A one-stage design is used. A total of 34 participants will be entered on this study. The expected accrual is 1-2 participants per month. If at least 91% (31) of evaluable participants achieve complete responses, the treatment will be considered promising and worthy of further study. Patients removed from study prior to initial restaging for reasons other than disease progression are not considered evaluable for response. The study has 91% power and 0.09 one-sided type I error to test a CR rate of 95% vs. a CR rate of 81%. With 34 eligible patients the 90% confidence interval for the true response rate will be no wider than 30%. If greater than 2 evaluable participants are seen not to have disease response (CR or PR) following brentuximab-AD therapy, the study will stop. Assuming the null response rate of 81%, the study will stop early with a maximum probability of 0.97. Under the promising rate, the study will stop early with a maximum probability of 0.24.

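### The only safety endpoint stops at grade IV, so whether a fatal toxicity counts rests on an undefined discontinuation limb or on a separate grade III/IV record

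*Combined protocol and SAP*

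**What the plan says.** The secondary objective (section 1.3) is to describe safety and tolerability. One endpoint serves it, in section 1.4.2: "Rate of grade III and IV adverse events or discontinuation due to toxicity". Sections 13.1.2 and 13.1.3 say that everyone treated is assessed for toxicity. They do not say which grades count or what a discontinuation due to toxicity is.

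Elsewhere the protocol treats death as a grade of its own. Section 10.4.1 lists grade 4 (life-threatening or disabling) and grade 5 (fatal) separately. The table of "Treatment-emergent adverse events" in section 6.1.1 pools grades 3 and above and gives grade 5 its own column.

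Section 2.1 describes the precedent: "We conducted a phase 2 study of 34 patients with non-bulky limited stage classical Hodgkin lymphoma", and in that trial "One additional patient developed neutropenic sepsis and died in remission during therapy".

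**The concern.** The objective is descriptive, so the endpoint definition decides what the safety result shows. The grade limb ends one step short of the worst outcome. If neither limb catches a death, that patient counts as free of the endpoint, whereas the same event, survived at grade IV, would have counted. The rationale in section 2.3 is a better toxicity profile with less neutropenia and neuropathy. An endpoint that supports that claim should plainly count a fatal neutropenic infection and not leave it to whoever codes the case.

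Failure-free survival does not fill the gap, because its definition in section 13.1.2 does not name death in remission as a failure.

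**Working it through.** **1. The plan's own figures.** No stated figure depends on this endpoint, but the design was checked so that the fix can be judged against it. Inputs from section 13.1.1: n = 34, success at 31 or more complete responses, null rate 0.81, target rate 0.95.

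- Type I error = P(X ≥ 31 | n = 34, p = 0.81) = 0.0906 (stated 0.09).
- Power = P(X ≥ 31 | n = 34, p = 0.95) = 0.9119 (stated 91%).

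Both reproduce at the printed precision. They depend on response counts only, so widening the adverse event grades changes neither.

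**2. The grade limb.** Section 10.4.1 keeps grades 4 and 5 apart, and section 13 does not widen the range. Read literally, an event recorded as grade 5 is outside the range III to IV.

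**3. The discontinuation limb.** Section 5.2 lists unacceptable adverse events, and section 5.3 lists toxicity, as reasons to stop treatment. Death is in neither list. It appears in section 5.5, as a reason for removal from the study. The text does not settle whether a toxic death on treatment is coded as a discontinuation due to toxicity or only as removal by death.

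**4. The four cases.**

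| Toxic death | Separate grade III/IV event recorded? | Grade limb | Discontinuation limb | Counted? |
|---|---|---|---|---|
| During treatment | Yes | Met | Unsettled | Yes |
| During treatment | No, grade 5 only | Not met | Unsettled | Depends on coding |
| After last planned dose | Yes | Met | Nothing left to discontinue | Yes |
| After last planned dose | No, grade 5 only | Not met | Nothing left to discontinue | No |

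The last row can occur. Section 6 collects adverse events until the final study visit, and section 8.3 places the post-treatment visit 6 weeks (± 3 days) after the last dose for those who complete treatment.

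**5. Size per missed death.** Section 13.1.1 states that "A total of 34 participants will be entered on this study". If all 34 are treated, one missed death lowers the rate by 1/34 = 2.9 percentage points. For example, 11/34 = 32.4% would be reported as 10/34 = 29.4%. This is a maximum per death, because a death that counts by another route costs nothing.

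**6. How often a toxic death might occur.** The documents give one event in 34 from the previous trial: 2.9%, exact 95% confidence interval 0.1% to 15.3%. With an assumed true rate p, the chance of at least one toxic death among 34 is 1 − (1 − p)^34:

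| Assumed p | At least one toxic death |
|---|---|
| 1% | 29% |
| 2% | 50% |
| 1/34 | 64% |
| 5% | 83% |

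These are chances that a toxic death occurs, by any route and at any time. The chance that the endpoint misses one is smaller and cannot be estimated from the documents.

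**The case against.** The strongest reply is that the endpoint has two limbs. A patient who dies of sepsis during therapy has stopped treatment because of toxicity, and the endpoint asks only for the cause of stopping, not whether death is on a list. Section 10.2 also puts all adverse events on the case report forms, so such a patient may well have a separate grade III or IV record, such as neutropenia. This stands. A reader might infer that a toxic death can never be an event under this endpoint, and the documents do not support that. The patient in the previous trial died during therapy, so even that case is not the clear miss. What remains is that the answer depends on coding during treatment and that nothing covers the last row of the table of cases.

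A reader might also infer that only exploratory overall survival would show a toxic death. That is not so. Section 13.1.4 has a response category (number 6) for early death from toxicity, section 10.4.1 requires grade 5 events to be reported, and section 11.2 allows deaths within 30 days to go to the monitoring committee. None of these is the safety endpoint, but the deaths are not lost.

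The rule that "Patients removed from study prior to initial restaging for reasons other than disease progression are not considered evaluable for response" is a separate matter. It concerns the response denominator, and rewording the safety endpoint would not change it.

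Two smaller points also stand. The section 6.1.1 table summarises earlier single-agent studies, so it shows a convention the authors reproduced and not a rule for this trial. And section 2.3 expects less neutropenia with this regimen, so carrying the previous trial's rate forward is only an assumption.

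**Conclusion.** The point holds as a defect in the endpoint definition. Grade 5 is outside the stated range. During treatment, a toxic death counts only through an undefined limb or a separate grade III/IV record. After the last planned dose, a fatal toxicity recorded only as grade 5 meets neither limb.

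The effect is at most 2.9 percentage points per missed death, assuming 34 treated participants. Replacements allowed by section 13.1.4 would make the step slightly smaller. The 64% should not be read as the chance of a missed death: it is the chance of any toxic death if the true rate is 1/34, and it rests on a single event.

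The endpoint has no hypothesis or threshold, so no trial decision turns on it. The change should still be made, because in a 34-patient trial the worst safety outcome should not be counted or left out by a coding choice.

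**What to change.** In section 1.4.2, define the endpoint as the proportion of treated participants with any grade 3 or higher (grade 3 to 5) adverse event or discontinuation due to toxicity. State that death from toxicity counts, whether it occurs during treatment or after the last dose, and report grade 5 events on their own line.

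The cost is a change of wording. Fatal events already go on the case report forms and serious adverse event forms, so no new data are needed. Type I error, power and sample size stay as they are. The only downside is that the reported toxicity rate may be slightly less favourable.

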## **2. BACKGROUND**

### **2.1 Study Agent(s)**

- 2.1.1 Brentuximab Vedotin (SGN-35, Adcetris)

Brentuximab vedotin is an anti-CD30 antibody-drug conjugate (ADC) consisting of an IgG1 antibody against CD30 bound to the anti-microtubule agent monomethyl auristatin E (MMAE). There have been two phase II studies of single agent brentuximab in relapsed/refractory cHL and relapsed/refractory systemic anaplastic large cell lymphoma (ALCL). In the pivotal phase II study of cHL 102 patients received brentuximab at 1.8 mg/kg every 3 weeks. This patient population was heavily pre-treated with a median of 3.5 prior treatments. Seventy-five percent of patients had an objective response (complete or partial remission) with median duration of approximately 9 months. Thirty-four percent of patients achieved a complete response (CR). In the phase II study of relapsed or refractory ALCL 38 patients received brentuximab also at 1.8 mg/kg every 3 weeks. Seventy-two percent of patients were ALK negative (which typically carries a poor prognosis) and patients had received a median of 2 prior systemic therapies. The objective response rate (ORR) was 86% with CR obtained in 53% of patients (median duration of response not yet reached). Nearly all patients (>90%) in both studies experienced a reduction in tumor volume. A phase I study evaluated the combination of brentuximab vedotin with either ABVD or AVD (without bleomycin). The bleomycin-containing arm was found to induce excess pulmonary toxicity, but brentuximab with AVD was found to be overall well tolerated with excellent efficacy in patients with advanced stage disease. The recommended phase II dose for brentuximab combined with AVD is 1.2 mg/kg every 2 weeks.

Brentuximab has been well tolerated in clinical trials to date (see section 6.1). Treatment-associated adverse events (AEs) occurring in  $\geq 20\%$  of patients in the phase II studies combined include peripheral sensory neuropathy (44%), fatigue (42%), nausea (41%), diarrhea (34%), pyrexia (31%), upper respiratory tract infection (28%), neutropenia (21%), and vomiting (20%). These events were primarily Grade 1 or 2, with the exception of neutropenia, for which Grade 3 and grade 4 events were reported for 13% and 7% of patients, respectively. Importantly, most of the peripheral sensory neuropathy events were reversible. Also, of note, similar patterns and incidences of AEs were generally observed for HL and ALCL patients.

Brentuximab pharmacokinetics were as follows. After an intravenous (IV) dose of 1.8 mg/kg every 3 weeks, maximum concentrations were typically observed at the end of infusion. A multi-exponential decline in brentuximab antibody-drug conjugate (ADC) serum concentrations was observed with a terminal half-life of approximately 4 to 6 days. Exposures were approximately dose proportional. Steady-state was achieved by 21 days, consistent with the terminal half-life estimate. Minimal to no accumulation was observed with multiple doses at the q3wk (every 3 weeks) schedule. The primary treatment-related effects of repeat-dose brentuximab administration to rats and monkeys were bone marrow hypocellularity and lymphoid depletion. The no-observed-adverse-effect level (NOAEL) for repeat-dose administration of brentuximab was 0.5 and 1 mg/kg in rat and monkey, respectively. The highest nonseverely toxic dose (HNSTD) for repeat-dose administration of brentuximab was 5 and 3 mg/kg in rat and monkey, respectively. In up to one-month repeat-dose toxicity studies of brentuximab in rats at doses up to 15 mg/kg, the following target organs were identified: bone marrow (hypocellularity), thymus (lymphoid depletion), spleen (lymphoid depletion), liver (focal coagulative necrosis), intestine

(single cell necrosis), testis (seminiferous tubular degeneration), and lung (alveolar histiocytosis) in rat only. Following a 4-week recovery period, all target organ toxicity was reversible except for testicular toxicity. Testicular toxicity in rat was partially resolved following a 16-week off-treatment recovery phase.

Based on the above data, the Oncology Drug Advisory Committee voted unanimously on 7/14/11 to recommend brentuximab vedotin be FDA-approved for relapsed classical Hodgkin Lymphoma and anaplastic large cell lymphoma.

We conducted a phase 2 study of 34 patients with non-bulky limited stage classical Hodgkin lymphoma, which completed accrual in 2014. Though data are immature, the treatment appeared highly effective and overall well tolerated. Preliminarily, all patients achieved complete response after 2 cycles of combination brentuximab-AD and no patients required more than 4 cycles of combination chemotherapy. One patient did relapse after achieving remission and was successfully treated with second-line therapy. One additional patient developed neutropenic sepsis and died in remission during therapy. An initially high rate of neutropenic fever was observed, prompting a protocol amendment requiring the use of GCSF support, after which the incidence of infection and neutropenic fever was much lower.

## 2.2 Hodgkin Lymphoma

Over the last 40+ years advances in the treatment Hodgkin Lymphoma have led to a remarkable improvement in the long-term outcomes of what was once considered an incurable disease. Classical Hodgkin lymphoma (cHL) now carries one of the most favorable prognoses in oncology with patients with limited stage disease achieving cure rates greater than 85%. Combined modality therapy has long been the standard of care for limited stage disease, though treatment paradigms continue to evolve with current efforts focused on preserving high rates of cure while minimizing potentially devastating late effects of radiation and chemotherapy including secondary malignancies and end organ damage such as heart and pulmonary disease.

In the last decade there have been a number of publications describing the long-term outcomes of patients treated with combined modality therapy (i.e. chemotherapy plus radiation) and chemotherapy alone, with similarly excellent results reported in patients with non-bulky limited stage disease. Studies of radiation-containing strategies demonstrate a continued risk of treatment-related morbidity and mortality due to second malignancies and cardiovascular disease well after the risk of HL relapse has peaked. For example, in an analysis of 1,474 patients treated at age less than 41, a significant increase of myocardial infarction (35.7 excess cases per 10,000 pt/y) and congestive heart failure (25.6 excess cases per 10,000 pt/y) were seen in patients treated with mediastinal radiation. These risks were greatly increased if radiation was combined with an anthracycline. In a retrospective review of 1,080 patients with stage IA-IIIB disease treated between 1969 and 1997, there was a relative risk of death from secondary cancers of 10-14.5, and from cardiac causes of 2.8 to 4.5.

Given these adverse late outcomes there have been efforts to de-escalate therapy with the hope of reducing toxicity while maintaining high cure rates. A strategy employing 4-6 cycles of ABVD (Adriamycin, Bleomycin, Vinblastine and Dacarbazine) with or without radiation in limited stage disease found no difference in overall survival between these groups at 5 years of follow-up. Analysis of this randomized trial at 12 years, however, demonstrated an improved overall survival in patients treated with 4-6 cycles of ABVD alone over combined modality therapy due to increased late events in patients treated with radiation. Chemotherapy alone yielded a favorable 12 year overall survival of 94%. Multiple other prospective and retrospective analyses have further validated ABVD chemotherapy alone in non-bulky limited stage cHL.

While a chemotherapy alone approach is appealing, the standard ABVD regimen is not without toxicity. Pulmonary toxicity from Bleomycin is the major non-hematologic toxicity of ABVD with incidence of pneumonitis ranging from 8-14%, and may result in treatment-related mortality. Neutropenia is also common, and may be worse when brentuximab vedotin is added to AVD, based on a high rate of neutropenic fever observed in our phase 2 trial prompting addition of routine growth factor support. We also observed a significant rate of peripheral neuropathy, likely related to the combination of vinblastine and brentuximab vedotin, both of which cause neuropathy due to activity on microtubules.

The German Hodgkin Study group explored whether Bleomycin and Dacarbazine are required to preserve the efficacy of this combination by comparing ABVD, AVB, AVD, and AV. In the final analysis, the omission of Dacarbazine resulted in a significantly inferior outcome, and omission of bleomycin also resulted in a slightly inferior PFS compared to AVD and ABVD. Another attempt to eliminate both bleomycin and dacarbazine in a phase II CALGB trial of AVG (Adriamycin, Vinblastine and Gemcitabine) in non-bulky limited stage patients, however, resulted in disappointing efficacy with a CR rate of 72.7% and 3-year PFS of 77%. These experiences suggest that a more potent anti-lymphoma therapy would need to be added in order to omit bleomycin with preserved efficacy.

### **2.3 Rationale**

The clinical efficacy of the ABVD regimen is likely to be preserved or improved by adding brentuximab, the single most active agent ever identified in Hodgkin lymphoma, while eliminating the Bleomycin will remove the potentially devastating risk of bleomycin lung injury. Given the overlapping mechanism of action of vinblastine and brentuximab vedotin targeting microtubules, we hypothesize that substituting brentuximab for vinblastine will preserve efficacy while improving the toxicity profile with a reduction in neutropenia and peripheral neuropathy. We are therefore conducting this phase II trial of brentuximab in combination with AD (Adriamycin and Dacarbazine) as initial therapy for non-bulky limited stage cHL.

